7.7 Post-study anticancer therapy status

The investigator or qualified designee will review all new anti-neoplastic therapy initiated after the last dose of trial treatment. If a subject initiates a new anti-cancer therapy within 30 days after the last dose of trial treatment, the 30 day Safety Follow-up visit must occur before the first dose of the new therapy. Once new anti-cancer therapy has been initiated the subject will move into survival follow-up.

7.8 Safety Follow-Up Visit: 30 days (± 15 days) post discontinuation

The mandatory Safety Follow-Up Visit should be conducted approximately 30 days after the last dose of trial treatment or before the initiation of a new anti-cancer treatment, whichever comes first. All AEs that occur prior to the Safety Follow-Up Visit should be recorded. Subjects with an AE of Grade > 1 attributed to pembrolizumab or ferumoxytol will be followed until the resolution of the AE to Grade 0-1 or until the beginning of a new anti-neoplastic therapy, whichever occurs first. SAEs that occur within 90 days of the end of treatment or before initiation of a new anti-cancer treatment should also be followed and recorded. Subjects who are eligible for retreatment with pembrolizumab (as described in Section 7.9) may have up to two safety follow-up visits, one after the Treatment Period and one after the Second Course Phase.

7.9 Follow-up

Subjects who complete 2 years of treatment or 35 cycles (whichever comes later) will move into the Follow-Up Phase and should be assessed every 12 weeks (± 30 days) by clinical standard of care MRI scans and clinical assessment to monitor disease status for up to 1 year or until they progress or death. After 1 year, the imaging and clinical assessment time point will occur every 6 months (± 30 days) until death.

7.10 Survival Follow-up when off study

Once a subject is taken off study for any reason, the subject moves into the survival follow-up phase. Survival data will be collected from the medical record when available. When possible, the patient will be contacted by telephone approximately every 12 weeks to assess for survival status until death, withdrawal of consent, or the end of the study, whichever occurs first.

7.11 Second Course Phase (Retreatment Period)

Subjects who stop pembrolizumab with CR in the brain and systemically may be eligible for up to one year of additional pembrolizumab therapy if they progress systemically, but maintain a CR in the brain. This retreatment is termed the Second Course Phase of this study and is only available if the study remains open and the subject meets the following conditions:

Either

- Stopped initial treatment with pembrolizumab after attaining an investigator-determined confirmed CR, and
 - Was treated for at least 24 weeks with pembrolizumab before discontinuing therapy
 - Received at least two treatments with pembrolizumab beyond the date when the initial CR was declared

OR

- Had CR in the brain and systemically and stopped pembrolizumab treatment after 24 months of study therapy for reasons other than disease progression or intolerability

AND

- Experienced an investigator-determined confirmed radiographic disease progression after stopping their initial treatment with pembrolizumab
- Did not receive any anti-cancer treatment since the last dose of pembrolizumab
- Has a performance status of 0 or 1 on the ECOG Performance Scale
- Demonstrates adequate organ function as detailed in Section 5.2
- Female subject of childbearing potential should have a negative serum or urine pregnancy test within 72 hours prior to receiving retreatment with study medication.
- Female subject of childbearing potential should be willing to use 2 methods of birth control or be surgically sterile, or abstain from heterosexual activity for the course of the study through 120 days after the last dose of study medication. Subjects of child bearing potential are those who have not been surgically sterilized or have been free from menses for > 1 year.
- Male subject should agree to use an adequate method of contraception including but not limited to abstinence from heterosexual activity starting with the first dose of study therapy through 120 days after the last dose of study therapy.
- Does not have a history or current evidence of any condition, therapy, or laboratory abnormality that might interfere with the subject's participation for the full duration of the trial or is not in the best interest of the subject to participate, in the opinion of the treating investigator.

Subjects who restart treatment will be retreated at the same dose and dose interval as when they last received pembrolizumab. Treatment will be administered for up to one additional year.

Visit requirements are outlined in Section 6.0 – Schedule of Events.

7.12 Dose modification and toxicity management for immune-related AEs associated with pembrolizumab

Pembrolizumab

AEs associated with pembrolizumab exposure may represent an immunologic etiology. These immune-related AEs (irAEs) may occur shortly after the first dose or several months after the last dose of pembrolizumab treatment and may affect more than one body system simultaneously. Therefore, early recognition and initiation of treatment is critical to reduce complications. Based on existing clinical trial data, most irAEs were reversible and could be managed with interruptions of pembrolizumab, administration of corticosteroids and/or other supportive care. For suspected irAEs, ensure adequate evaluation to confirm etiology or exclude other causes. Additional procedures or tests such as bronchoscopy, endoscopy, skin biopsy may be included as part of the evaluation. Based on the severity of irAEs, withhold or permanently discontinue pembrolizumab and administer corticosteroids. Dose modification and toxicity management guidelines for irAEs associated with pembrolizumab are provided in Table 6.

Table 6 Dose Modification and Toxicity Management Guidelines for Immune-related AEs Associated with Pembrolizumab

General instructions:				

 1. Corticosteroid taper should be initiated upon AE improving to Grade 1 or less and continue to taper over at least 4 weeks. 2. For situations where pembrolizumab has been withheld, pembrolizumab can be resumed after AE has been reduced to Grade 1 or 0 and corticosteroid has been tapered. Pembrolizumab should be permanently discontinued if AE does not resolve within 12 weeks of last dose or corticosteroids cannot be reduced to ≤ 10 mg prednisone or equivalent per day within 12 weeks. 3. For severe and life-threatening irAEs, IV corticosteroid should be initiated first followed by oral steroid. Other immunosuppressive treatment should be initiated if irAEs cannot be controlled by corticosteroids. 				
Immune-related AEs	Toxicity grade or conditions (CTCAEv4.0)	Action taken to pembrolizumab	irAE management with corticosteroid and/or other therapies	Monitor and follow-up
Pneumonitis	Grade 2	Withhold	
 • Administer corticosteroids (initial dose of 1-2 mg/kg prednisone or equivalent) followed by taper 	
 • Monitor participants for signs and symptoms of pneumonitis • Evaluate participants with suspected pneumonitis with radiographic imaging and initiate corticosteroid treatment • Add prophylactic antibiotics for opportunistic infections
	Grade 3 or 4, or recurrent Grade 2	Permanently discontinue		
Diarrhea / Colitis	Grade 2 or 3	Withhold	
 • Administer corticosteroids (initial dose of 1-2 mg/kg prednisone or equivalent) followed by taper 	
 • Monitor participants for signs and symptoms of enterocolitis (ie, diarrhea, abdominal pain, blood or mucus in stool with or without fever) and of bowel

	Grade 4	Permanently discontinue		
perforation (ie, peritoneal signs and ileus).
 
 Participants with \geq Grade 2 diarrhea suspecting colitis should consider GI consultation and performing endoscopy to rule out colitis. Participants with diarrhea/colitis should be advised to drink liberal quantities of clear fluids. If sufficient oral fluid intake is not feasible, fluid and electrolytes should be substituted via IV infusion.
AST / ALT elevation or Increased bilirubin	Grade 2	Withhold	
 Administer corticosteroids (initial dose of 0.5- 1 mg/kg prednisone or equivalent) followed by taper 	
 Monitor with liver function tests (consider weekly or more frequently until liver enzyme value returned to baseline or is stable)
	Grade 3 or 4	Permanently discontinue	
 Administer corticosteroids (initial dose of 1-2 mg/kg prednisone or equivalent) followed by taper 	
Type 1 diabetes mellitus (T1DM) or Hyperglycemia	Newly onset T1DM or Grade 3 or 4 hyperglycemia associated with evidence of β -cell failure	Withhold	
 Initiate insulin replacement therapy for participants with T1DM Administer anti-hyperglycemic in participants with hyperglycemia 	
 Monitor participants for hyperglycemia or other signs and symptoms of diabetes.
Hypophysitis	Grade 2	Withhold	
 Administer corticosteroids and initiate hormonal replacements as clinically indicated. 	
 Monitor for signs and symptoms of hypophysitis (including hypopituitarism and adrenal insufficiency)
	Grade 3 or 4	Withhold or permanently discontinue ¹		
Hyperthyroidism	Grade 2	Continue	
 Treat with non-selective beta-blockers (eg, propranolol) or thionamides as appropriate 	
 Monitor for signs and symptoms of thyroid disorders.
	Grade 3 or 4	Withhold or permanently discontinue ¹		
Hypothyroidism	Grade 2-4	Continue	
 Initiate thyroid replacement hormones (eg, levothyroxine or liothyronine) per standard of care 	
 Monitor for signs and symptoms of thyroid disorders.
Nephritis and Renal dysfunction	Grade 2	Withhold	
 Administer corticosteroids (prednisone 1-2 mg/kg or equivalent) followed by taper. 	
 Monitor changes of renal function
	Grade 3 or 4	Permanently discontinue		
Myocarditis	Grade 1 or 2	Withhold	
 Based on severity of AE administer corticosteroids 	
 Ensure adequate evaluation to confirm etiology and/or exclude other causes
	Grade 3 or 4	Permanently discontinue		

All other immune-related AEs	Intolerable/ persistent Grade 2	Withhold	
Based on type and severity of AE administer corticosteroids	
Ensure adequate evaluation to confirm etiology and/or exclude other causes
	Grade 3	Withhold or discontinue based on the type of event. Events that require discontinuation include and not limited to: Gullain-Barre Syndrome, encephalitis		
	Grade 4 or recurrent Grade 3	Permanently discontinue		
1. Withhold or permanently discontinue pembrolizumab is at the discretion of the investigator or treating physician.				
NOTE: For participants with Grade 3 or 4 immune-related endocrinopathy where withhold of pembrolizumab is required, pembrolizumab may be resumed when AE resolves to \leq Grade 2 and is controlled with hormonal replacement therapy or achieved metabolic control (in case of T1DM).				

Table 7 below shows treatment guidelines for subjects who experience an infusion reaction associated with administration of pembrolizumab.

Table 7: Infusion Reaction Treatment Guidelines

NCI CTCAE Grade	Treatment	Premedication at Subsequent Dosing
Grade 1 Mild reaction; infusion interruption not indicated; intervention not indicated	Increase monitoring of vital signs as medically indicated until the subject is deemed medically stable in the opinion of the investigator.	None
Grade 2 Requires therapy or infusion interruption but responds promptly to symptomatic treatment (e.g., antihistamines, NSAIDs, narcotics, IV fluids); prophylactic medications indicated for ≤24 hrs	Stop Infusion. Additional appropriate medical therapy may include but is not limited to: IV fluids Antihistamines NSAIDs Acetaminophen Narcotics Increase monitoring of vital signs as medically indicated until the subject is deemed medically stable in the opinion of the investigator. If symptoms resolve within 1 hour of stopping drug infusion, the infusion may be restarted at 50% of the original infusion rate (e.g. from 100 mL/hr to 50 mL/hr). Otherwise dosing will be held until symptoms resolve and the subject should be premedicated for the next scheduled dose. Subjects who develop Grade 2 toxicity despite adequate premedication should be permanently discontinued from further study drug treatment	Subject may be premedicated 1.5h (± 30 minutes) prior to infusion of pembrolizumab with: Diphenhydramine 50 mg po (or equivalent dose of antihistamine). Acetaminophen 500-1000 mg po (or equivalent dose of analgesic).
Grades 3 or 4 Grade 3: Prolonged (i.e., not rapidly responsive to symptomatic medication and/or brief interruption of infusion); recurrence of symptoms following initial improvement; hospitalization indicated for other clinical sequelae (e.g., renal impairment, pulmonary infiltrates) Grade 4: Life-threatening; pressor or ventilatory support indicated	Stop Infusion. Additional appropriate medical therapy may include but is not limited to: Epinephrine** IV fluids Antihistamines NSAIDs Acetaminophen Narcotics Oxygen Pressors Corticosteroids Increase monitoring of vital signs as medically indicated until the subject is deemed medically stable in the opinion of the investigator. Hospitalization may be indicated. **In cases of anaphylaxis, epinephrine should be used immediately. Subject is permanently discontinued from further study drug treatment.	No subsequent dosing
Appropriate resuscitation equipment should be available at the bedside and a physician readily available during the period of drug administration. For further information, please refer to the Common Terminology Criteria for Adverse Events v4.0 (CTCAE) at http://ctep.cancer.gov		

Dosing delays of up to 7 days are permitted at physician discretion for medical / surgical events or logistical reasons. Dosing interruptions (missing a dose) are permitted in the case of medical / surgical events or logistical reasons not related to study therapy (e.g., elective surgery, unrelated medical events, subject vacation, and/or holidays), not to exceed two consecutive doses or a maximum of 9 weeks. The reason for interruption will be documented in the subject's study record.

There is limited data regarding optimal therapy for refractory and/or persistent side effects from pembrolizumab (after discontinuation of pembrolizumab and initiation of steroids). These subjects will be managed as per treating physician's discretion in consultation with the pembrolizumab clinical team at Merck & Co. This may include but not limited to the use of drugs such as infliximab (5 mg/kg). If symptoms persist after the first infliximab dose, a second dose of infliximab (5 mg/kg) may be repeated two weeks after the initial dose.

7.13 Dose Modifications for Ferumoxytol and Temozolomide

[figure not shown]
Ferumoxytol

There will be no dose limitations or modifications to ferumoxytol. If subject experiences a grade 2 or greater allergic or anaphylactic reaction (CTCAE v 4.0) that is directly attributable to the ferumoxytol, the subject will be removed from study.

Temozolomide (arm 2 only)

Temozolomide will be administered as described in section 7.6 with standard dose modifications per the product prescribing information (Section 14.4. Subject may remain on study and continue on pembrolizumab if temozolomide is stopped.

In the concomitant setting (daily during radiation) the dose of temozolomide will be 75mg/m² per day. Dose will be held for ANC less than 1000/ μ L or platelet count less than 100,000/ μ L and the dose will be held until ANC is over 1000/ μ L or platelet count over 100,000/ μ L. In the adjuvant setting (monthly after completing radiation), dosage of temozolomide must be adjusted according to nadir neutrophil and platelet counts in the previous cycle and neutrophil and platelet counts at the time of initiating the next cycle. The initial dose is 150 mg/m² orally once daily for 5 consecutive days per 28-day treatment cycle. Temozolomide dose may be increased to 200 mg/m² /day for 5 consecutive days per 28-day treatment cycle. The general algorithm for dose adjustment is as follows:

Additionally, for subjects in arm 2 who will receive temozolomide and pembrolizumab, although there is no concern for overlapping toxicities, in cases where attribution to one drug of the other is unclear, the dose of pembrolizumab will be modified or discontinued based on the guidelines in table 6. If the toxicity resolves appropriately, pembrolizumab will be restarted. Temozolomide will be modified or discontinued at the discretion of the treating physician

Radiation

Radiation will be administered as described in section 7.4. Subject may remain on study and continue on pembrolizumab and/or temozolomide if radiation is stopped for toxicities attributed to radiation.

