4.3 Preclinical and Clinical Trial Data

Refer to the Investigator's Brochures/Package Inserts for Preclinical and Clinical data (Supplemental Material, section 15).

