Ferumoxytol has provided improved imaging with minimal safety concerns even using extremely high doses in preclinical trials with animals, in vitro using human blood cells, and in multiple IND sponsored studies. Ferumoxytol has few systemic reactions and can be given as a bolus for MRA analysis of tumor vasculature. The ferumoxytol Investigator's brochure 2012 contains detailed information of preclinical and clinical safety studies as summarized below.

Temozolomide for patients with glioblastoma (arm 2) will be as per clinical standard of care.

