9.6.1 Expected AEs from Temozolomide

See product insert (section 14.4). Adverse events and toxicities will be managed per institutional and accepted standard of care practices.

Table 9 Evaluating Adverse Events

An investigator who is a qualified physician, will evaluate all adverse events as to:

V4.0 CTCAE Grading	Grade 1	Mild; asymptomatic or mild symptoms; clinical or diagnostic observations only; intervention not indicated.
	Grade 2	Moderate; minimal, local or noninvasive intervention indicated; limiting age-appropriate instrumental ADL.
	Grade 3	Severe or medically significant but not immediately life-threatening; hospitalization or prolongation of hospitalization indicated; disabling; limiting self-care ADL.
	Grade 4	Life threatening consequences; urgent intervention indicated.
	Grade 5	Death related to AE
Seriousness	A serious adverse event is any adverse event occurring at any dose or during any use of Merck product that:	
	† Results in death ; or	
	† Is life threatening ; or places the subject, in the view of the investigator, at immediate risk of death from the event as it occurred (Note: This does not include an adverse event that, had it occurred in a more severe form, might have caused death.); or	
	† Results in a persistent or significant disability/incapacity (substantial disruption of one's ability to conduct normal life functions); or	
	† Results in or prolongs an existing inpatient hospitalization (hospitalization is defined as an inpatient admission, regardless of length of stay, even if the hospitalization is a precautionary measure for continued observation. (Note: Hospitalization [including hospitalization for an elective procedure] for a preexisting condition which has not worsened does not constitute a serious adverse event.); or	
	† Is a congenital anomaly/birth defect (in offspring of subject taking the product regardless of time to diagnosis); or	
	Is a new cancer ; (that is not a condition of the study) or	
	Is an overdose (whether accidental or intentional). Any adverse event associated with an overdose is considered a serious adverse event. An overdose that is not associated with an adverse event is considered a non-serious event of clinical interest and must be reported within 24 hours.	

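### Section 7.13: the rule for restarting concomitant temozolomide joins the two counts with *or*, so read literally a hold can end while one count is still below its limit

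*Combined protocol and SAP*

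**What the plan says.** Section 7.13 sets the rule for the phase introduced by "In the concomitant setting (daily during radiation) the dose of temozolomide will be" 75 mg/m² per day. One sentence contains two clauses.

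- **Hold:** "Dose will be held for ANC less than 1000"/μL, or for platelets below 100,000/μL.
- **Release:** "the dose will be held until ANC is over 1000"/μL "or platelet count over 100,000"/μL.

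Section 7.6 sends the reader to 7.13 for temozolomide dose modifications, so this is the operative text. The temozolomide part of 7.13 opens by deferring to the product's prescribing information. Section 4.3.2 states "Temozolomide for patients with glioblastoma (arm 2) will be as per clinical standard of care", and section 9.6.1 adds "Adverse events and toxicities will be managed per institutional and accepted standard of care practices".

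The next sentence of 7.13 concerns the adjuvant phase. It ties dosing to the nadir counts of the previous cycle and to "neutrophil and platelet counts at the time of initiating the next cycle". No visible section says that both counts must recover before concomitant dosing resumes.

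**The concern.** *Or* is right for starting a hold, because either low count is reason enough. In the release clause the same word makes either adequate count reason enough to stop holding. The logical opposite of *either is low* is *neither is low*, and that needs *and*.

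The rule covers a myelosuppressive drug scheduled daily for six weeks (Table 4) in an arm of 43 glioblastoma subjects. At stake is whether a subject with one recovered count and one low count is treated as still on hold. The entry criteria make this situation plausible. Table 3 admits subjects with platelets of 100,000/mcL, which is exactly the hold limit, whereas the ANC floor of 1,500/mcL lies 500 above its hold limit. A subject who enters at the platelet floor becomes platelet-low with any fall, and the ANC may stay above 1000.

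**Working it through.** The plan states no figure to reproduce. The check is one of logic.

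**Inputs, all from section 7.13.** Let A be ANC per μL and P be platelets per μL.

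- Hold: A < 1000 or P < 100,000.
- Release as written: A > 1000 or P > 100,000.

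**Step 1: when are both clauses true?** A count cannot be below and above its own limit at once. Both clauses are therefore true exactly when one count is below its limit and the other is above its limit.

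**Step 2: what should release be?** The negation of the hold rule is A ≥ 1000 *and* P ≥ 100,000. Only this form is the exact complement of the hold rule.

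**Step 3: compare the rules on example counts.**

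| ANC | Platelets | Hold | Release as written | *and* with over | *and* with at least |
|---|---|---|---|---|---|
| 800 | 80,000 | yes | no | no | no |
| 1200 | 80,000 | yes | **yes** | no | no |
| 800 | 120,000 | yes | **yes** | no | no |
| 1000 | 120,000 | no | yes | **no** | yes |
| 1200 | 100,000 | no | yes | **no** | yes |
| 1000 | 100,000 | no | no | **no** | yes |
| 1200 | 120,000 | no | yes | yes | yes |

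- **Both counts low, one recovers (row 1 to row 2).** At 800 and 80,000 the dose is held and the clauses agree. When ANC reaches 1200 the release wording is met, although platelets are still at 80,000 and the hold clause still applies.
- **One count low from the start (row 2 or row 3).** Release is satisfied at the moment the hold begins, so on the literal wording the hold has no effect.
- **Changing only the connective (rows 4 to 6).** This removes the conflict but leaves a gap. A subject already on hold stays on hold when a count sits exactly at its limit, although nothing then meets the hold rule. Replacing *over* with *at least* closes the gap.

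The rows are logical cases. They are not weighted by how often they occur and give no estimate of frequency.

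**The case against.** The strongest reply is that nobody would follow the literal reading. The two clauses are parallel, and the ordinary sense is distributive: whichever count caused the hold must recover. A reading that ends a single-count hold as it starts makes the rule pointless, so it is the reading least likely to be acted on. Section 7.13 also defers to the prescribing information, and sections 4.3.2 and 9.6.1 defer to standard practice. This largely stands, and it is why the point is minor. It does not make the sentence correct, because the sentence says neither *both* nor *respectively*. The prescribing information is not reproduced, so its content cannot be used to settle the reading.

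A reader might infer that the protocol gives sites two opposite orders, or tells them to dose a subject with a low count. The text does not go that far. The release clause only marks the end of a hold. It never directs that temozolomide be given, and the hold clause continues to apply to any count still below its limit.

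A reader might also look to the rest of 7.13 for an answer. The adjuvant sentence names both counts but governs another phase. A dose-adjustment algorithm is announced after it and is not visible in the text reviewed. Its absence is not a fault of the plan, and since it is introduced within the adjuvant text, nothing shows that it corrects the concomitant rule. The treating-physician discretion later in 7.13 is written for toxicity whose attribution to temozolomide or pembrolizumab is unclear, not for count recovery.

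**Conclusion.** The release clause is wrong as written. On its literal wording, recovery of either count ends a hold while the other is still below its limit, and this conflicts with the hold clause in the same sentence.

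It is a minor dosing-safety correction for a standard-of-care drug, confined to the concomitant phase of the glioblastoma arm. How many subjects could be affected cannot be derived, because the documents give no cytopenia rates for this regimen. A reader might infer consequences for adverse event attribution, the precision estimates or the rCBV sensitivity and specificity analysis. Nothing in the documents supports that, and none is claimed.

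The conclusion rests on the visible sentence alone. It assumes that the part of 7.13 not shown contains no concomitant-phase rule that overrides it.

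**What to change.** In section 7.13, reword the release clause so that the concomitant dose is held until ANC is at least 1000/μL *and* platelet count is at least 100,000/μL. The numerical limits stay as they are. The edit changes one connective and replaces *over* with *at least* for both counts. It can go into the next amendment, with no change to data collection or analysis.

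A separate clerical tidy-up carries no weight in this point. References to the temozolomide insert as section 14.4 (in 7.13 and 9.6.1) or 14.5 (in 4.3.5 and 11.0) should read 15.5. Section 14 concerns inclusion of women, minorities and children, and section 4.3 already points to "Clinical data (Supplemental Material, section 15".
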